- Not enrolled in special education for mental retardation, autism or severe behavior disorders.
- Primary diabetes caregiver not diagnosed or in treatment for major depression, psychosis, bipolar disorder or substance use disorder within the 6 months prior to enrollment; Child not in an inpatient psychiatric unit or day treatment program during the 6 months prior to enrollment.
- Family has working telephone service.

The objective is to enroll 150 youths with T1DM with HbA_{1C} above target despite treatment with intensified T1DM regimens. *We limited enrollment to youths with $HbA_{1C} \geq 7.5\%$ and $\leq 10.0\%$ since they have much to gain in terms of improved glycemic control, reduction of health care costs and deferral of complications. Youths with $HbA_{1C} < 7.5\%$ have different goals for adding CGS to diabetes care, such as decreased severe hypoglycemia and glycemic variability rather than reduction in HbA_{1C} , while those with $HbA_{1C} > 10.0\%$ may be unable to use CGS safely.* Inclusion of two sub-samples with differing primary outcomes would create analytic problems that are avoided with a more homogeneous sample. The JDRF Artificial Pancreas Project will enroll a sub-sample of patients with $HbA_{1C} < 7.0\%$, while our study will make a unique contribution by focusing on adolescents with suboptimal glycemic control.

5.3. Stratified randomization *Youths entering the study must have been on a T1DM regimen for ≥ 6 months comprising either a "basal-bolus" multiple daily injection (MDI) or continuous subcutaneous insulin infusion (CSII; insulin pump) regimens using carbohydrate counting and insulin correction factors. To promote equality of the groups in HbA_{1C} , randomization will be stratified by two HbA_{1C} levels: $\leq 8.8\%$ and $> 8.8\%$. Separate*

randomization lists will be used for each center and HbA_{1c} stratum. After the baseline evaluation, adolescents within each stratum will be randomized with equal probability to the three groups (SC, CGS or CGS+BT) so that each center randomizes similar numbers into each group and so that the groups are similar in HbA_{1c}.

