Glucose Monitoring System Rating Questionnaire This instrument was developed for the JDRF Artificial Pancreas Project to permit direct comparison of conventional SMBG using a home glucose meter to conventional SMBG augmented by use of a CGS device. By contrast, the CGM Satisfaction Scale⁵⁶⁻⁵⁷ was constructed by DirecNet to obtain participants' ratings of satisfaction with and impact of CGS devices that they had used for 3 months. The 25 items were drawn from the earlier 44-item CGM Satisfaction Scale and reworded such that participants rate the glucose monitoring system they are using (SMBG with or without CGS). Preliminary data from the JDRF trial show that the revised instrument has equally sound psychometric properties as the CGM Satisfaction scale, with the added advantage of enabling direct comparisons of SMBG and CGS within and between patients. Alpha coefficients were $.93$ for parents and $.89$ for youths. Parent-Youth agreement was $r = .61$. Test-retest reliability was $.71$ for parents and $.59$ for youths at 3 months.

Blood Glucose Monitoring Communication Questionnaire This is an 8-item scale on which respondents describe their communication and affect about SMBG data.⁷⁹ It is a three-choice Likert scale, with higher scores indicating more frequent negative affect around SMBG. Internal consistency was $.77$ for 153 youths and $.82$ for parents, parent and adolescent scores correlated significantly, and 1-year test-retest reliability was $.70$. Scores correlated significantly with HbA_{1c}, diabetes-related conflict and quality of life. This measure will enable assessment of the extent to which provision of CGS data impacts emotional reactions to glucose levels and evaluation of the moderation of CGS treatment benefits as a function of scores on this measure.

Hypoglycemia Fear Survey This scale⁸⁴⁻⁸⁵ measures worry and behavior related to hypoglycemia. Separate parent and youth versions have been validated.⁸⁴⁻⁸⁵ This measure will clarify if CGS use affects anxiety related to hypoglycemia. *Since the content of this measure emphasizes aversion to experienced hypoglycemia rather than apprehension about its occurrence, we have added four items to evaluate this latter construct.*

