Statistical analysis will begin with treatment of missing data, preliminary descriptive analysis and visual inspection of distributions.¹⁵⁵⁻¹⁵⁶ Appropriate transformations of variables will be used to restore normality if needed. Baseline values of the primary outcome and predictor variables will be compared to determine if there are significant pretreatment differences between the groups that require adjustments. Visual examination of scatter plots, histograms and other graphical summaries will be used to identify possible associations or treatment effects of interest. Where multiple statistical comparisons are planned, we will make appropriate multiplicity adjustments.¹⁵⁵⁻¹⁵⁸ Internal consistency will be calculated for each psychometric measure based on

data from this study and only those with $\alpha \geq .70$ will enter data analyses. Upon completion of these preparatory activities, we will apply Individual Growth Modeling¹⁶⁰⁻¹⁶¹ to test the hypotheses listed below (see Section 5.12 for details).

5.10. Hypotheses. The following hypotheses, corresponding to the three specific aims, will be tested:

Hypothesis 1: Adolescents in CGS+BT will show more improvement in glycemic control (HbA_{1C}, Kovatchev's measures of glycemic variability derived from SMBG and CGS data, and proportion of CGS values in the normal range) compared with those in SC and CGS over the 9-month Randomized Phase.

Hypothesis 2: Adolescents in CGS+BT will realize more improvement in diabetes-related behavioral outcomes (Diabetes Self-Management Profile; PedsQL Diabetes Module; Diabetes Responsibility and Conflict Scale; Hypoglycemia Fear Survey; Blood Glucose Monitoring Communication Questionnaire: Blood Glucose Monitoring System Rating Questionnaire) compared with those in SC and CGS and in scores on the CGM Satisfaction Scale (CGS vs CGS+BT only) over the 9-month randomization phase of the study.

Hypothesis 3a: Improvements in HbA_{1C} during the 9-month Randomized Phase will be moderated by adolescents' and parents' baseline status on the following measures: Socioeconomic status; Family composition; Adolescent age; Diabetes Problem Solving Interview, Parent-Adolescent Relationship Questionnaire; Diabetes Family Responsibility Questionnaire; Wiebe Parental Supportive Involvement Interview; and Diabetes Responsibility and Conflict Scale).

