The level-2 models are used to test whether time-invariant predictors are related to the initial status and the change of the outcome over time. The treatment effect in this study will be coded as a dummy variable, a time-invariant predictor of change to be evaluated in the level-2 models. Other examples of time-invariant predictors include socioeconomic status, parent marital status, and gender that are thought to be stable over time, and will be tested as the moderators of the treatment effect. Specifically, the level-2 models are

$$\begin{aligned}\pi_{0i} &= \beta_{00} + \beta_{01} * X_i + \mu_{0i} \\ \pi_{1i} &= \beta_{10} + \beta_{11} * X_i + \mu_{1i}\end{aligned}$$

where β_{00} and β_{10} are the grand means for the intercepts and the slopes estimated in the level-1 model, respectively. β_{01} and β_{11} are regression coefficients for X_i which is a time-invariant variable for subject i , with μ_{0i} and μ_{1i} the random errors in the models. When X_i is the treatment effect coded as a dummy variable, a significant β_{01} indicates that the outcome variable is different for the treatment groups at the baseline. Our major research interest is to evaluate coefficient β_{11} ----- a significant β_{11} shows that the change in the outcome variable is different for treatment groups due to the intervention program.

Both the basic level-1 and level-2 models in IGM can be extended by including more variables in the models. In general, variables measured repeatedly over time, also referred to as time-varying or within-subject variables, are included in level-1 models. The between-subject variables, also referred to as time-invariant variables and usually only measured at baseline, are included in level-2 models. The shape of the curves for the outcome variables will be determined first. Time-invariant and time-varying predictors will then be examined for their relationship with the outcome using the estimated growth factors of the trajectories. The 3 primary hypotheses proposed in this study will be evaluated within the IGM framework. SAS Proc Mixed and Proc Glimmix will be used for the IGM analysis for the 3 primary hypotheses.

Hypothesis 1: Adolescents in CGS+BT will show more improvement in glycemic control (HbA_{1c}; Kovatchev's measures of glycemic variability derived from SMBG and CGS data; Proportion of CGS values in the normal range) compared with those in SC and CGS over the 9-month Randomized Phase.

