To evaluate the treatment effects on the change of glycemic control over time, HbA_{1c} measured from baseline to end of study will be the outcome variable in the level-1 model. A participant without missing values will have a total of 5 measures of HbA_{1c}. The time interval between baseline and the measure of each HbA_{1c} in the unit of months will be the Time variable in the level-1 model. The shape of the HbA_{1c} trajectory will be determined statistically by comparing a linear model and a quadratic model using the AIC and BIC indices produced by SAS Proc Mixed. In level-2 models, X_i will be a dummy variable indicating treatment groups. For example, to evaluate the treatment effects between CGS+BT and CGS groups, the dummy variable will be coded 1 for CGS+BT and 0 for CGS. A significant coefficient of the dummy variable will indicate that the change rate of HbA_{1c} over time is different for the two groups due to the treatment effect. A similar strategy will be applied to evaluate the difference in the change of HbA_{1c} between CGS+BT and SC, and CGS and SC groups. Since Kovatchev's measures of glycemic variability and the proportion of CGS values in the normal range are on continuous scales that are comparable across repeated measures, these variables are also appropriate to use as outcome variables with IGM estimated using SAS Proc Mixed.

If the treatment groups are significantly different in the outcome measures, it is of interest to examine whether the difference in treatment groups persists after adjusting the covariates that are known to be associated with the outcome. This process will be conducted by including covariates in the IGM framework. For example, demographic variables (SES, parent marital status, etc.) and disease variables (diabetes onset age, duration, etc.) can be included in the models as covariates to improve the precision of estimation when evaluating the treatment effect. If the dummy variable is still significant with the covariates in the model, the interpretation is that the treatment accounts for some unique variance in the change of the outcome over time above and beyond the effects of the covariates. The effect of site difference will be included as a between-subject covariate with a random effect. Specific programming to include the site difference as a random effect using SAS Proc Mixed will follow Dmitrienko et al for clinical trial data collected from multiple sites.¹⁶²

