To adjust for the effects of important covariates in examining the treatment effect, the covariates will be included in level-1 and level-2 models. The time-varying covariates will be included in the level-1 model and the time-invariant covariates will be in level-2 models. There are two advantages of adjusting the covariates when evaluating the treatment effect. First, the adjusted analysis will improve the power of evaluating the treatment effect because of increased precision of estimation.¹⁶³⁻¹⁶⁵ By adjusting a covariate in a linear model, the precision gained is proportional to the correlation between the covariate and the outcome variable. Second, omitting important covariates in the model may lead to bias of the results. Therefore, important covariates will be included in the models to evaluate the group difference in all the outcomes. Similar to the strategies in Primary Hypotheses 1, the effect of site difference will be treated as an additional between-subject variable as a random effect in the models.

Hypothesis 3a: Improvements in HbA_{1c} during the 9-month Randomized Phase will be moderated by adolescents' baseline status on the following measures: Socioeconomic status; Family composition; Adolescent age; Parent-Adolescent Relationship Questionnaire; Diabetes Family Responsibility Questionnaire; Wiebe Parental Supportive Involvement Interview; and Diabetes Responsibility and Conflict Scale).

Analysis of moderator effects can identify variables that are predictive of intervention outcomes. . For example, in Hypothesis 3a, if the treatment effect on HbA_{1c} differs as a function of the family's socioeconomic status, then socioeconomic status is a moderator variable. It is important to evaluate the heterogeneity of the treatment effect to identify the subgroups that derive lesser or greater benefit from the intervention.

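### The growth model estimates and tests arm differences at baseline and does not prespecify baseline adjustment; a common baseline mean would give a modest precision gain at no cost.

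*Combined protocol and SAP*

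**What the plan says.** Section 5.12 models the level-2 intercept as β00 + β01·X, where X is the treatment dummy. Each arm therefore has a free baseline mean, and a significant β01 "indicates that the outcome variable is different for the treatment groups at the baseline". The effect of interest is β11, the arm difference in slope; a significant value "shows that the change in the outcome variable is different for treatment groups due to the intervention program". Baseline HbA1c is the first of the five responses.

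The plan describes adjustment in several ways:
- **Section 5.9:** baseline values of the primary outcome and predictors are compared "to determine if there are significant pretreatment differences between the groups that require adjustments".
- **Section 5.12, Hypothesis 1:** "If the treatment groups are significantly different in the outcome measures, it is of interest to examine whether the difference in treatment groups persists" once covariates are added. Site enters as a random effect with no such condition.
- **Section 5.12, Hypothesis 2:** "important covariates will be included in the models to evaluate the group difference in all the outcomes". The covariates are not listed.

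Under Section 5.3, "adolescents within each stratum will be randomized with equal probability to the three groups", with strata formed by center and by HbA1c split at 8.8%. Section 5.8 places the baseline evaluation before randomization. The analysis sections do not name the HbA1c stratum or the baseline outcome value as a covariate.

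**The concern.** Baseline is measured before assignment and assignment is random within strata, so the arms have the same true baseline mean. A significant β01 can only be a chance finding. If that test decides whether to adjust, the data choose the model. Estimating β01 also spends information on a quantity known to be zero, so β11 is estimated less precisely than it could be.

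The three covariate rules add to this. One is triggered by baseline imbalance, one by a significant treatment effect, and one is unconditional but has no list. Two analysts could follow the plan and fit different models.

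What is at stake is precision and prespecification, not validity.

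**Working it through.** **Method.** Let I = X′V⁻¹X be the per-arm information for intercept and slope. With β01 free, the per-arm slope variance is the slope element of I⁻¹. With a common baseline mean and equal arms, it is 1 divided by the slope element of I. Two-sided α = 0.05 is assumed, because Section 5.13 states none.

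**1. HbA1c: the plan's own figure first.** Inputs from Section 5.13: a 0.8% difference at 12 months, SD rising from 1.2 to 1.5 (taken as linear), visits at 0/3/6/9/12 months, and 50 per arm falling to 45 and then 40. No within-patient correlation is given.
- Comparing only the 12-month means (0.8/1.5) gives power 66.5% (n = 40), 71.6% (n = 45) or 76.0% (n = 50).
- The plan's 94.5% is for the longitudinal model. With β01 free, that model reaches 94.5% at a baseline-to-12-month correlation of about 0.58-0.70, under compound symmetry, AR(1) or random slopes with intercept-slope correlation 0 to 0.5. With that correlation at -0.2 it does not (maximum about 92%). So 94.5% is attainable but cannot be verified.
- Example: compound symmetry r = 0.642, dropout 50→45→40. The SE of the 12-month slope contrast is 0.2247 with β01 free and 0.2201 with a common baseline. The variance ratio is (0.2201/0.2247)² = 0.96, and power goes from 94.5% to 95.3%.

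| HbA1c, covariances giving 94.5% | Variance cut | Power |
|---|---|---|
| Months 0-12, 0.8% | about 2-7% | 94.5% → 94.8-95.8% |
| Months 0-12, 0.6% (SC vs CGS) | about 2-7% | 76.1% → 76.8-79.0% |
| Months 0-9 only, same slope as 0.8% | about 1-11% | up by 0.4-4.7 points |

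The gain is larger if correlation is weaker than 94.5% implies. Under AR(1) with adjacent-visit correlation 0.4-0.7 the months 0-12 variance ratio is 0.54-0.74, but those covariances do not give the stated power.

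**2. Hypothesis 2 questionnaires.** Section 5.5 gives test-retest values for two of the six instruments: .71 (parents) and .59 (youths) at 3 months for the Glucose Monitoring System Rating Questionnaire, and "1-year test-retest reliability was $.70" for the Blood Glucose Monitoring Communication Questionnaire. For visits 0/3/6/9, Σt = 18, Σt² = 126 and Σ(t − t̄)² = 45. Under compound symmetry with unit SD:
- β01 free: month-9 slope contrast variance per arm = 81(1−r)/45 = 1.8(1−r).
- Common baseline: 81(1−r)/[126 − 324r/(1+3r)].
- Ratio = 45/[126 − 324r/(1+3r)].

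At r = .59 the bracket is 126 − 69.0 = 57.0, so the ratio is 0.790. Power is for an illustrative 0.5 SD effect at month 9 with 45 per arm; the plan gives no effect size for these scales.

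| r | Variance cut | Equivalent extra patients | Power, free → common |
|---|---|---|---|
| .59 | 21.0% | 1/0.790 − 1 = 27% | 78.8% → 87.4% |
| .70 | 14.8% | 17% | 89.8% → 93.8% |
| .71 | 14.3% | 17% | 90.7% → 94.4% |

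**3. Sensitivity to the covariance.** The level-2 slope equation has its own random error, so compound symmetry is only one possibility. With intercept reliability .59-.71 and an assumed random-slope SD of 0.25-1.0 baseline SD over 9 months, the cut is:
- 19-27% at intercept-slope correlation -0.3;
- 5-19% at zero correlation;
- near 0% to 14% at correlations of 0.3 to 0.5.

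Under AR(1), another candidate structure in Section 5.12, it is 41% at adjacent-visit r = .59 and 33% at .70-.71.

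**The case against.** A free-intercept growth model is standard and valid. Baseline is in the response vector, so chance imbalance is already removed from β11. On HbA1c, the outcome the trial is powered on, the gain is about one power point. All of this stands, and it limits the point to efficiency and prespecification.

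Four stronger readings are tempting, and the documents do not support them:
- *The plan adjusts only if a baseline test is significant.* Section 5.9 does not say only. Site enters regardless, and the Hypothesis 2 text includes unlisted covariates without that test. The accurate criticism is that the rules differ and the list is open.
- *Baseline information is thrown away, or the contrast is biased.* Neither follows when baseline is the first response.
- *The slope contrast is no better than a raw change score.* Under compound symmetry its variance is 1.8(1−r) per arm against 2(1−r) for the 9-month change, which is 10% lower even with β01 free.
- *All Hypothesis 2 scales have correlations of .59-.71.* Section 5.5 gives such values for only two of the six.

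A further fair objection is that the HbA1c stratum is baseline HbA1c dichotomized. Adding it to a model in which baseline HbA1c is a response conditions on a function of that response, so the stratum needs different handling for HbA1c.

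**Conclusion.** The point holds as a free improvement of modest size. The baseline test is uninformative under this randomization, baseline adjustment is not prespecified, and the covariate rules in Sections 5.9 and 5.12 need reconciling. No bias in the treatment contrast is shown.

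For HbA1c the loss is small wherever the stated power holds, and it rises only if the analysis is confined to the 9-month Randomized Phase or the correlation is weaker. The questionnaire gain may be material, but it could be close to nil with random slopes positively correlated with the intercept. The sizes rest on assumed covariances and two-sided α = 0.05; the questionnaire power figures also rest on the illustrative 0.5 SD effect. A common baseline did not increase the variance in any scenario tried.

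**What to change.** For every Hypothesis 1 and 2 outcome, prespecify one three-arm model with center and either a common baseline mean (β01 = 0) or the baseline value as a covariate of the post-baseline responses. Apply it whatever imbalance is observed.

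Add the HbA1c stratum for outcomes other than HbA1c. For HbA1c, let baseline HbA1c itself carry that information.

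Delete the baseline significance comparison in Section 5.9 and the interpretation of β01 in Section 5.12, and report baseline data descriptively by arm. Replace the differing covariate rules in Sections 5.9 and 5.12 with one rule and a named covariate list.

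The cost is analysis-plan wording; no patients, visits or data are added.

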The IGM approach allows for comparison and selection of the appropriate covariance structure of the outcome measured over time. Candidate structures include compound symmetry (CS), autoregressive order-1 AR(1), unstructured, and AR(1) with random effect which will be specified in SAS Proc Mixed. The AIC and BIC indices will be used for model selection, with smaller AIC or BIC values indicating relatively better models fitting the data. The selection of an appropriate covariance structure may further reduce the bias of model estimation.

Hypothesis 2: Youths in CGS+BT will realize more improvement in diabetes-related behavioral outcomes (Diabetes Self-Management Profile; PedsQL Diabetes Module; Diabetes Responsibility and Conflict Scale; Hypoglycemia Fear Survey; Blood Glucose Monitoring Communication Questionnaire; Blood Glucose Monitoring System Rating Questionnaire) compared with those in SC and CGS over the 9-month randomization phase of the study.

The data analysis strategy to evaluate Hypothesis 2 will be similar to that applied to Hypothesis 1 within the IGM framework. Specifically, in the level-1 model the outcome variables will be the Diabetes Self-Management Profile, the PedsQL Diabetes Module, the Diabetes Responsibility and Conflict Scale, the Hypoglycemia Fear Survey, the Blood Glucose Monitoring Communication Questionnaire, and the Blood Glucose Monitoring System Rating Questionnaire. The Time variable in the level-1 model will be the time interval from baseline to the time of measurement in month. In level-2 models, a dummy variable indicating treatment groups will indicate the treatment effect. A significant coefficient of the dummy variable will show that the change rate of the outcome is different for the treatment groups due to the treatment program.

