center at Nemours-Jacksonville. Should any of these materials be lost, it will not be possible for others to identify the participant. Digital audio recordings of CGS+BT intervention visits will contain the participants' voices and are therefore potentially identifiable. All of the measures planned for collection in the proposed study have been used in the principal investigator's prior research without significant concerns being expressed by any participants. None of these measures seek participants' responses about potentially stigmatizing, embarrassing or illegal behaviors, thoughts or attitudes.

8.5. Assessment of research-related benefits: All patients who enroll in the study will receive intensive therapy for T1DM and may therefore achieve better glycemic control. Our Intensive Therapy patients achieved mean HbA_{1c} levels of 7.6%-7.7% that emerged after 3 months of treatment and remained near that level. Patients who are randomized to either CGS or CGS+BT may achieve lower HbA_{1c} levels than those in the SC condition and/or they may experience fewer episodes of severe hypoglycemia. SC participants will be allowed to use a CGS device during the 3-month continuation phase of the study. Assuming that all CGS's used in the study will have FDA approval for such therapeutic indications by the end of the study, all participants in the study will be allowed to keep their CGS's after the study. In order to continue using the device after the study, participants would then assume responsibility for the costs of purchasing additional sensors.

8.6. Safeguards to protect against risks: The most important risks faced by patients in the proposed study are possible deterioration in glycemic control and possible increased occurrence of severe hypoglycemia.

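### The HbA1c trajectory shape is chosen from the trial data, but the treatment test is defined only for the linear shape, and no month-9 contrast is prespecified

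*Combined protocol and SAP*

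**What the plan says.** Section 5.12 writes a level-1 model for linear change, with Time in months from baseline, and level-2 equations for the intercept and the linear slope only. The treatment dummy enters both. The plan names its coefficient in the slope equation, beta11, as the main interest: a significant value "shows that the change in the outcome variable is different for treatment groups due to the intervention program".

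The order of work is also given: "The shape of the curves for the outcome variables will be determined first", with predictors examined afterwards through the estimated growth factors. Under Hypothesis 1 the shape is settled by "comparing a linear model and a quadratic model using the AIC and BIC indices produced by SAS Proc Mixed". For the covariance structure the same approach is used: "The AIC and BIC indices will be used for model selection". After the shape is chosen, the test is still described as a single coefficient: "A significant coefficient of the dummy variable will indicate that the change rate of HbA_{1c} over time is different for the two groups". The example given is pairwise: "the dummy variable will be coded 1 for CGS+BT and 0 for CGS".

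Hypothesis 1 concerns the 9-month Randomized Phase. The model uses all five HbA1c measures, to month 12, and Section 5.1 offers CGS to all three groups after month 9. There is no level-2 equation for a quadratic factor, no joint test, no recentring of Time, no contrast at month 9, and no rule for when AIC and BIC disagree. Section 5.12 lists not comparing means at specific time points as an advantage of the method.

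**The concern.** In a quadratic model with arm-specific curvature, the arm difference at time t is beta11 × t + beta21 × t². Because Time is zero at baseline, beta11 is then the difference in slope at month 0. It says nothing by itself about month 9. The only treatment coefficient that the plan names would therefore change meaning with a choice made from the trial data, and the plan does not say which test replaces it.

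A curved path is plausible. Section 8.5 reports HbA1c levels in the earlier Intensive Therapy group "that emerged after 3 months of treatment and remained near that level", and Section 5.8 expects CGS+BT to reach its level and keep it. What is at stake is the test of the primary hypothesis. Depending on how the gap is filled after the data are seen, the same trial could miss a real month-9 benefit, report one that is absent, or misstate its size.

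**Working it through.** **Inputs from Section 5.13:** SD 1.2 at baseline and 1.5 at month 12; difference CGS+BT versus CGS of 0.8 at month 12 (0.0667 per month if linear, so 0.6 at month 9); 50 per arm enrolled, 45 at month 9.

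**Assumptions, because the documents give none:** two-sided 5% test; residual variance s² = 0.20 to 0.30; zero intercept-slope covariance; 47 per arm with complete visits, to stand for 45-50. The slope variance is then τ² = (1.5² − 1.2²)/144 = 0.81/144 = 0.005625. Power is Φ(|d|/SE − 1.96); the other tail is negligible except where d is near zero.

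**The plan's own figure.** The stated power is 94.5%. A plain comparison at month 12 (0.8, SD 1.5) gives only 66%, 72% and 76% with 40, 45 and 50 per arm, so the figure must be a slope test. For visits 0, 3, 6, 9, 12 the squared deviations of time from its mean sum to 90, and

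SE² (linear beta11) = (2/47)(τ² + s²/90), so SE = 0.0183 to 0.0195.

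Power is 0.0667/SE = 3.65 to 3.42, or 95% to 93%. The stated 94.5% is attainable, though it cannot be confirmed without the residual variance used.

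**Arm-specific quadratic, beta11 read alone.** Here beta11 = mid-period slope − 12 × beta21, and Var(beta21) per subject is s²/1134, so

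SE² = (2/47)(τ² + s²/90 + 144 s²/1134), giving SE = 0.0376 to 0.0448.

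Under the same linear effect, 0.0667/SE = 1.77 to 1.49: power 43% to 32%.

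**Month-9 contrast from that same quadratic.** 9 beta11 + 81 beta21 = 9 × mid-period slope − 27 beta21, so

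SE² = (2/47)[81(τ² + s²/90) + 729 s²/1134], giving SE = 0.180 to 0.198 and power 91% to 86%. The information is in the model; beta11 alone does not use it.

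**Other paths.** With complete visits the fitted coefficients are simple weighted sums.

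- *Plateau, 0.6 from month 3 on.* Linear beta11 = 0.6 × (−3 + 0 + 3 + 6)/90 = 0.040, so 9 × beta11 = 0.36. A quadratic term common to the arms leaves this unchanged, because the arm difference is still fitted by intercept and slope only. For the arm-specific quadratic, beta21 = 0.6 × (−1 − 2 − 1 + 2)/14/9 = −0.00952, so beta11 = 0.040 + 12 × 0.00952 = 0.154 and 9 × beta11 = 1.39.
- *Transient, 0.8, 0.5, 0, 0 at months 3, 6, 9, 12 (an illustration; the plan projects no such path).* Mid-period slope = −2.4/90 = −0.0267; beta21 = (−0.8 − 1.0)/14/9 = −0.0143; beta11 = −0.0267 + 0.1714 = 0.145.

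| True arm difference | At month 9 | 9 × beta11, linear or common quadratic | 9 × beta11, arm-specific quadratic | Month-9 contrast, arm-specific quadratic |
|---|---|---|---|---|
| Linear, 0.8 at month 12 | 0.6 | 0.60; 93-95% | 0.60; 32-43% | 0.60; 86-91% |
| Plateau from month 3 | 0.6 | 0.36; 54-59% | 1.39; 93-98% | 0.62; 88-93% |
| Transient | 0 | −0.24; 28-31% | 1.30; 90-97% | 0.15; 11-13% |

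Percentages are the chance of a significant result.

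**How often would a quadratic be picked if the truth is linear?** With two extra parameters, AIC needs a chi-square above 4: e^(−2) = 13.5%. BIC needs one above 2 ln N: 1/N, about 1% for N = 94.

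**The case against.** A reader might infer that the plan keeps its test on beta11 after a quadratic pick. It does not say so. Beta11 is defined under the linear model, and Section 5.12 adds that the models can be extended and that predictors are examined through the growth factors, in the plural. The fair description is an undefined test.

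A reader might also infer that the test generally loses most of its power. The 32-43% needs a linear truth, a quadratic pick (about 13.5% by AIC, about 1% by BIC), arm-specific curvature, and beta11 read alone. In the plateau case the quadratic beta11 has more power than the linear one; its fault there is that it overstates the effect more than twofold. If the quadratic term is common to the arms, as the written level-2 equations would allow, beta11 stays a constant slope difference and loses no power under a linear truth.

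A third tempting inference is that the three pairwise comparisons would rest on different shapes. The pairwise coding is introduced as an example and the trajectory shape is referred to in the singular, so the documents do not support this. Nothing excludes it either.

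Finally, the earlier-trial plateau is the course of one arm after starting intensive therapy, whereas all participants here have been on intensified regimens for at least 6 months. It makes curvature plausible, but does not show curvature in the difference between arms.

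These points narrow the concern without removing it. The common-quadratic reading helps only if the arm difference is a straight line, and a linear pick is no safe default: it also includes month 12, after all arms have been offered CGS.

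**Conclusion.** The concern holds as a gap in the primary test. The shape is data-selected, the test after a quadratic pick is undefined, and beta11 is not the 9-month effect on any reading once the arm difference departs from a straight line over the five visits. For a 0.6% difference reached early and held, the readings of 9 × beta11 run from 0.36 to 1.39.

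The power figures rest on the assumed residual variance of 0.20-0.30, zero intercept-slope covariance, 47 complete cases per arm and a two-sided 5% level. The change in meaning of beta11, and the 0.36 and 1.39, do not depend on the residual variance. The documents do not support saying that the plan has chosen the wrong test; they support saying that it has not chosen one for the quadratic case and has none aimed at month 9.

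**What to change.** State that, whatever shape or covariance is selected, the primary test for each pair of arms is the contrast in HbA1c change from baseline to month 9, estimated from one model containing all three arms. Either form would serve:

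- visit as a categorical factor with arm-by-visit terms and unstructured covariance; or
- a growth model with one prespecified shape and arm-specific time terms, with the month-9 contrast written out. This keeps individually varying visit times, but is still an approximation: in the transient example it returns 0.15 where the truth is 0.

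Keep data-selected growth shapes as secondary, and say how a disagreement between AIC and BIC is settled.

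The cost is wording plus a little power. For the categorical contrast, SE² = (2/47)(81τ² + 2s²), so SE = 0.191 to 0.212, and a true 0.6 at month 9 is detected with 88% to 81% power. If the effect is truly linear, the slope over months 0-9 has 83-90% (SE² = (2/47)(τ² + s²/45)) and the five-visit slope 93-95%. The power statement in Section 5.13 should be redone for the contrast adopted.
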